# STUDY SYNOPSIS

Location of study: University of New Mexico Hospital, Pediatric/Adult Pulmonary Clinic, Ambulatory Care Center, Albuquerque, NM		Tabulated Study Protocol	
Finished product:  13C-urea Breath Test Kit			
Active ingredient:  13C-urea			
Protocol date HRPO#		Planned study period	
29 November 2012   12-521		January1, 2013-March 31,2013	

## **Title of Study:**

A Dose-escalation Study to Detect Urease-producing Bacteria in Lungs of Healthy Volunteers and Subjects with Cystic Fibrosis Using Aerosolized C-urea

**Indication:** Use of a C-urea breath test in the qualitative detection of urease-containing bacteria in the respiratory tract and as an aid in the initial and post-treatment detection of respiratory tract infections

**Study Design:** This is a single-center, single-administration, dose-escalation study designed to determine the safety and dose response of aerosolized C-urea 20 mg and 50 mg in detecting urease-producing bacteria in the lungs of healthy volunteers (those without and those diagnosed with *Helicobacter pylori* infection) and in subjects with cystic fibrosis (CF). Subjects will be contacted by telephone the next day and asked a non-leading question about adverse events.

The dose will not be escalated until at least 24 hours after all subjects in the cohort have been tested at the current dose. If a subject has an adverse event or new symptom that remains unresolved at 48 hours, no new subjects will be enrolled until the relationship between the AE and symptom can be evaluated. If any subject experiences an adverse event considered by the data safety monitor to be dose limiting, then three additional subjects will be enrolled at that current dose. Dose escalation will stop if more than one additional subject experiences dose-limiting toxicity.

After the safety of the maximum dose in the cohort of healthy volunteers without *H. pylori* infection has been reviewed by a data safety monitor, healthy volunteers diagnosed with *H. pylori* infection and subjects with CF will be enrolled. Three subjects diagnosed with *H. pylori* infection will be tested at the maximum dose to assess potential interference of urease producing bacteria in the stomach; subjects infected with *H. pylori* can be enrolled at any time after the safety of the maximum dose in healthy volunteers without *H. pylori* infection has been evaluated, but they will meet the entrance criteria for healthy volunteers without *H. pylori* infection.

Sputum will be collected from each subject with CF before administering study drug in order to identify bacterial flora using two standard microbiologic methods. The first is a quantitative method in which colonies are stained and counted, the second is a colorimetric method in which a sample is plated in a medium that changes to a blue color as its pH is increased by the production of ammonia, a by-product of the urease-catalyzed degradation of urea.

**Study Duration:** The maximum duration of study participation for each subject is approximately 9 days: up to 7 days between the screening visit and the study visit plus a follow-up visit 24 hours after study drug administration.

Location of study: University of New Mexico Hospital, Pediatric/Adult Pulmonary Clinic, Ambulatory Care Center, Albuquerque, NM		Tabulated Study Protocol	
Finished product:  13C-urea Breath Test Kit			
Active ingredient:  13C-urea			
Protocol date HRPO#		Planned study period	
29 November 2012 12-521		January1, 2013-March 31,2013	

**Study Objectives:** The primary objective is to assess the safety of C-urea administered by inhalation. The secondary objective is to assess the kinetics of C-carbon dioxide production by measuring the isotopic ratio of C to C in exhaled carbon dioxide up to 15 minutes after administration and to assess potential interference of urease-producing bacteria in the stomach.

**Study Endpoints:** The primary endpoint is the safety of inhaled C-urea assessed by adverse events including pulmonary findings and changes from baseline in physical examination findings, pulse oximetry results, pulmonary function test results, and vital signs. Secondary endpoints are the isotopic ratios of C to C in exhaled carbon dioxide measured with the POCone detector (Meretek Diagnostics Group of Otsuka America Pharmaceutical, Rockville, MD) at 5, 10, and 15 minutes after study drug administration.

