# 3.1.3 Study Design

This is a single-center, single-administration, dose-escalation study designed to determine the safety and dose response of aerosolized C-urea 20 mg and 50 mg in detecting urease-producing bacteria in the lungs of healthy volunteers (those without and those diagnosed with *H. pylori* infection) and in subjects with CF. Subjects will be contacted by telephone the next day and asked a non-leading question about adverse events.

The dose will not be escalated until at least 24 hours after all subjects in the cohort have been tested at the current dose. If a subject has an adverse event or new symptom that remains unresolved at 48 hours, no new subjects will be enrolled until the relationship between the AE and symptom can be evaluated. If any subject experiences an adverse event considered by the data safety monitor to be dose limiting, then three additional subjects will be enrolled at that

current dose. Dose escalation will stop as described in Table 1 if more than one additional subject experiences dose-limiting toxicity (DLT) (Section 3.1.3.1).

After the safety of the maximum dose in the cohort of healthy volunteers without *H. pylori* infection has been reviewed by a data safety monitor, healthy volunteers diagnosed with *H. pylori* infection and subjects with CF will be enrolled. Three subjects diagnosed with *H. pylori* infection will be tested at the maximum dose to assess potential interference of urease producing bacteria in the stomach; subjects infected with *H. pylori* can be enrolled at any time after the safety of the maximum dose in healthy volunteers without *H. pylori* infection has been evaluated, but they will meet the entrance criteria for healthy volunteers without *H pylori* infection. Subjects will be discharged from the study site after 30 minutes or thereafter when oxygen saturation levels and FEV1 values return to baseline and coughing symptoms are resolved. Supportive treatment for symptom resolution, if needed, will be recorded on the case report form (CRF).

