**Table 1 Dose Escalation Rules** 

Condition within 24 hours after administration of study drug	Number of DLTs/ Subjects in Cohort	Action
If no subject experiences DLT	0/3	Enroll three subjects at the 50 mg dose level
If one subject experiences DLT	1/3	Enroll three additional subjects at the 20 mg dose
If no additional subject experiences DLT	1/6	Enroll three subjects at the 50 mg dose level
If more than one subject experiences DLT	>1/6	Stop enrollment

Subjects will be receive C-urea 20 mg and 50 mg unless enrollment stops because of DLT. DLT Dose-limiting toxicity.

Sputum will be collected from each subject with CF before administering study drug in order to identify bacterial flora using two standard microbiologic methods. The first is a quantitative method in which colonies are stained and counted, the second is a colorimetric method in which a sample is plated in a medium that changes to a blue color as its pH is increased by the production of ammonia, a by-product of the urease-catalyzed degradation of urea.

The pharmacokinetics of the production of C-carbon dioxide will be characterized by determining the isotopic ratio of C to C in exhaled carbon dioxide of subjects in each part before study drug administration and at 5, 10, and 15 minutes.

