# 5.1.6 Methods of Assigning Subjects to Treatment Group

Subjects without *H. pylori* infection will be assigned to a single, open-label treatment, beginning with the lower dose of study drug, in the order in which they enter the study according to the dose escalation rules in Table 1 (Section 3.1.3). Healthy volunteers diagnosed with *H. pylori* infection will received the MTD.

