# 5.1.8 Selection and Timing of Doses for Each Subject

Subjects will receive single doses of C-urea in increasing amounts, 20 mg in the first cohort and 50 mg in the second cohort as detailed in Table 1. Study drug may be administered in the fasted or as-fed state, but subjects should not ingest food until after the last breath sample is

collected; subjects may receive water *ad libitum*. Subjects may be administered study drug at any time of day with the provision they are required to be available 24 hours after the study drug is administered for a follow-up evaluation.

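### The prose escalation rules in the Synopsis and 3.1.3 disagree with Table 1 and 3.2.3: they do not stop escalation at 2/6 DLTs, and their expansion trigger has no upper DLT count

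*Protocol*

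**What the plan says.** **Prose rule.** The Synopsis (Study Design) states the expansion: "If any subject experiences an adverse event considered by the data safety monitor to be dose limiting, then three additional subjects will be enrolled" at the current dose. Section 3.1.3 repeats it ("then three additional subjects will be enrolled at that" dose). In both places the next sentence stops escalation when two or more of the *additional* subjects have a DLT. The 3.1.3 version adds a pointer to Table 1.

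**Table 1.** After 0/3 the study moves to 50 mg. After 1/3 the action is "Enroll three additional subjects at the 20 mg dose". After 1/6 the study moves to 50 mg. The last row reads "If more than one subject experiences DLT", with a printed count of >1/6 and the action "Stop enrollment".

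**Section 3.2.3.** Escalation stops once more than one subject at a dose level has had a DLT. The section does not say what happens to further enrolment at the same dose.

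**Sample-size text.** The Synopsis, 3.2.1 and 9.1 add three subjects at every dose level where a dose-limiting event occurs. Sections 3.2.1 and 9.1 then reach the maximum of 30 by supposing one subject with a DLT at each level.

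**Which rule assigns doses.** Section 5.1.6 assigns subjects without *H. pylori* infection "in the order in which they enter the study according to the dose escalation rules in Table 1", whereas volunteers with "infection will received the MTD". Section 5.1.8 gives "20 mg in the first cohort and 50 mg in the second cohort as detailed in Table 1". Under 8.5 the data safety monitor decides when dose levels may rise and when subjects may be enrolled.

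**The concern.** This is a first-in-human study of the inhaled test with safety as its primary objective, so the escalation rule is its main protective device. The protocol writes that rule more than once, and the versions give different actions on the same data.

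Two things are at stake. One is whether subjects go on to 50 mg after two of six had a DLT at 20 mg. The other is whether three more people receive a dose at which two or all of the first three had a DLT. The stop point also feeds the maximum tolerated dose (3.1.3.2), which 5.1.6 then assigns to the *H. pylori* cohort.

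**Working it through.** **Step 1. Reproduce the plan's own figures.** There are five cohorts: healthy 20 mg, healthy 50 mg, *H. pylori* 50 mg, CF 20 mg and CF 50 mg. Planned N = 5 × 3 = 15. Maximum N = 5 × 6 = 30. Both agree with 9.1. Expansion after 2/3 or 3/3 also ends at six per cohort, so the maximum of 30 does not show which trigger is meant.

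**Step 2. Set the rules side by side for DLTs at 20 mg.**

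| Outcome | Prose (Synopsis, 3.1.3) | Table 1 | 3.2.3 |
|---|---|---|---|
| 0/3 | escalate | escalate | no stop |
| 1/3, then 0/3 (1/6) | escalate | escalate | no stop |
| 1/3, then 1/3 (2/6) | **no stop** | **stop** (>1/6) | **stop escalation** |
| 1/3, then 2/3 or 3/3 | stop | stop | stop escalation |
| 2/3 or 3/3 at once | **three more at same dose** | condition wording says stop; no row with that count | stop escalation; silent on same-dose enrolment |

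The third row is a plain contradiction. The last row is a conflict on Table 1's condition wording and a gap on its printed count.

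At 50 mg, Table 1's expansion row does not apply as written because it names only 20 mg. The uncapped prose is then the only explicit expansion instruction. A rule that stops only escalation has no effect at 50 mg, because there is no higher dose.

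**Step 3. Size of the stop-rule difference.** The protocol gives no DLT rate, so p = 5%, 10%, 20% and 30% are assumptions. Let P0 = (1 − p)³ and P1 = 3p(1 − p)². To isolate this defect, expansion is taken to occur at exactly 1/3 under both rules.

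- Table 1: P(escalate) = P0 + P1 × P0
- Prose: P(escalate) = P0 + P1 × (P0 + P1)
- Difference = P1²

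For p = 10%: P0 = 0.729 and P1 = 0.243. Table 1 gives 0.729 + 0.243 × 0.729 = 0.9061. The prose gives 0.729 + 0.243 × 0.972 = 0.9652.

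| p | Table 1 | Prose | Difference (before rounding) |
|---|---|---|---|
| 5% | 0.9734 | 0.9918 | 0.0183 |
| 10% | 0.9061 | 0.9652 | 0.0590 |
| 20% | 0.7086 | 0.8561 | 0.1475 |
| 30% | 0.4943 | 0.6887 | 0.1945 |

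This applies to each step from 20 mg to 50 mg, once in healthy volunteers and once in CF.

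**Step 4. Size of the expansion difference.** The rules part when the first three subjects have at least two DLTs: P(≥2 of 3) = 1 − P0 − P1. If the prose were followed literally, expected extra exposures per cohort = 3 × that probability.

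| p | P(≥2 of 3) | Expected extra subjects |
|---|---|---|
| 5% | 0.00725 | 0.02 |
| 10% | 0.028 | 0.08 |
| 20% | 0.104 | 0.31 |
| 30% | 0.216 | 0.65 |

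The two tables measure different defects and should not be added.

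**The case against.** The strongest reply is that the intended rule is clear. Section 3.1.3 sends the reader to Table 1 for the stop, and 5.1.6 and 5.1.8 assign doses by Table 1. Section 9.1 appeals to standard Phase 1 designs with cohorts of three. Sections 3.2.1 and 9.1 follow the expansion sentence directly with a single-DLT case. No enrolment is automatic, since the monitor sees the data daily and decides. On this view, one or two clauses are loosely worded and nobody would be dosed wrongly.

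Much of this stands. Table 1 is the better candidate for the governing rule, and the monitor lowers the practical risk. But 3.2 describes the monitor's discretion as additional to the mandatory rules, so it does not reconcile them. Table 1 cannot settle everything either: its expansion row omits 50 mg, its stop count omits 2/3 and 3/3, and 5.1.6 does not send the *H. pylori* cohort to it.

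A reader might infer something stronger: that Table 1 expressly orders a stop at 2/3 and 3/3, so that prose and table flatly oppose each other there. The printed count of >1/6, in a row that follows the expansion row, allows it to be read as a post-expansion outcome only. Nor does 3.2.3 forbid same-dose expansion, because it speaks only of escalation. For 2/3 and 3/3 the documents therefore support a conflict of wording with a gap in the table, and no more.

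**Conclusion.** The point holds in two parts of unequal firmness.

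- **Stop rule (firm).** The prose does not stop escalation at 2/6, while Table 1 and 3.2.3 do. The chance of escalating is higher under the prose by about 2, 6, 15 and 19 percentage points at assumed DLT rates of 5%, 10%, 20% and 30%.
- **Expansion rule (depends on a literal reading).** The uncapped trigger matters in 0.7%, 2.8%, 10.4% and 21.6% of cohorts at the same rates, and only if the monitor allows the enrolment.

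Both sets of figures assume independent DLTs at a common rate within a cohort. With an isotonic solution, asthma excluded and albuterol given before dosing in CF, the low end of the range may be the more likely. The documents do not support inferring that subjects would in practice be dosed after 2/3 or 3/3. They show only that the written rules do not agree on it. The choice of a three-subject cohort design is not in question. The wording should be corrected.

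**What to change.** 1. **Expansion trigger** (Synopsis Study Design and Sample Size, 3.1.3, 3.2.1, 9.1): add three subjects only when *exactly one of the first three subjects in a cohort at a dose level has a DLT*.
2. **Stop trigger** (Synopsis, 3.1.3): replace the count of additional subjects by *more than one subject in total at that dose level in that cohort (2/3, 3/3 or >1/6)*. Without this step the prose would still permit escalation at 2/6.
3. **Table 1:** make the expansion row apply at both 20 mg and 50 mg, and label the stop row *2/3, 3/3 or >1/6*.
4. **Scope of the stop:** state that it means no further subjects in that cohort at that dose and no escalation to a higher dose. Any effect on other cohorts (*H. pylori* at the maximum tolerated dose, CF) is for the data safety monitor under 3.1.3.2 and 8.5. If the scope is left unnamed, two DLTs in the *H. pylori* cohort could be read as halting CF enrolment.

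The cost is a wording amendment with IRB review. Planned N stays at 15 and maximum N at 30, since each of the five cohorts still expands at most from three to six. With expansion fixed at exactly 1/3, the chance of escalating becomes the Table 1 figure at every assumed rate.

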#### **Study Population:**

Subjects who meet all the following inclusion and exclusion criteria are eligible to enroll in the study.

# Inclusion Criteria for Healthy Volunteers Without H. pylori infection:

Healthy volunteers who meet all the following inclusion criteria are eligible to enroll.

- At least 18 years old at the time of providing informed consent in a manner approved by the University of New Mexico, Institutional Review Board and willing to comply with the requirements of the study
- In generally good health as determined by the investigator, with no respiratory illness within 2 weeks before the screening visit and no pulmonary history
- No history of allergy or asthma
- Has not smoked tobacco within 6 months before the screening visit and agrees not to smoke until after the follow up visit
- Forced expiratory volume in 1 second (FEV1) at least 80% at the time of providing informed consent

# Inclusion Criteria for Healthy Volunteers Diagnosed With H. pylori infection:

Healthy volunteers diagnosed with *H. pylori* infection who meet all the inclusion criteria for healthy volunteers and additionally who have been diagnosed with *H. pylori* infection are eligible to enroll.

## **Inclusion Criteria for Subjects With Cystic Fibrosis:**

Subjects with CF who meet all the following inclusion criteria are eligible to enroll.

- At least 18 years old at the time of providing informed consent in a manner approved by the University of New Mexico, Institutional Review Board and willing to comply with the requirements of the study
- Diagnosed with CF at least 24 months before the screening visit

Location of study: University of New Mexico Hospital, Pediatric/Adult Pulmonary Clinic, Ambulatory Care Center, Albuquerque, NM		Tabulated Study Protocol	
Finished product:  13C-urea Breath Test Kit			
Active ingredient:  13C-urea			
Protocol date HRPO#		Planned study period	
29 November 2012 12-521		January1, 2013-March 31,2013	

- Documented presence of *Pseudomonas* organisms in at least three sputum cultures within 2 years before the screening visit, one of which within 6 months before the screening visit
- Is able to produce sputum at the time of the screening visit
- FEV1>60% or more than 1.5 L at the time of providing informed consent
- Has not smoked tobacco within 6 months before the screening visit and agrees not to smoke until after the follow up visit

### **Exclusion Criteria**

Subjects who meet any of the following exclusion criteria are not eligible to enroll.

- Positive *H. pylori* serology, except for subjects in the *H. pylori* cohort
- Subjects intolerant of albuterol
- Subjects diagnosed with asthma
- Subjects with evidence of upper respiratory tract infection within 14 days before the screening visit
- Use of inhaled antibiotics within 12 hours before the administration of the breath test on Day 1 or required use of inhaled antibiotics during the study
- Has smoked tobacco within 6 months before the screening visit
- Females who are pregnant or nursing or of child-bearing potential who are not using a medically acceptable form of contraception (acceptable forms of contraception are hormonal birth control, intrauterine device, or barrier method plus a spermicidal agent) or abstinence
- Any condition or history that, in the judgment of the investigator, would compromise the ability of the subject to comply with the study protocol or to complete the study
- Subjects who have used an investigational agent within 28 days before Day 1

# Study Product, Dose, and Mode of Administration:

C-urea: 20 mg and 50 mg administered by inhalation

Reference Product, Dose, and Mode of Administration: Not applicable

**Efficacy Variables:** Breath test results

**Safety Variables:** Adverse events (frequency, intensity, seriousness, and relationship to study drug), spirometry test results (FEV1 and FVC), and respiratory examinations (respiratory rate, auscultation [presence of wheezing and crackles], pulse oximetry, and related symptoms, such as cough)

**Pharmacokinetics:** Production of carbon dioxide

**Sample Size and Statistical Rationale:** Approximately 15 subjects will be enrolled, 9 healthy volunteers and 6 subjects with CF. Three healthy volunteers without *H. pylori* infection will each receive

Location of study: University of New Mexico Hospital, Pediatric/Adult Pulmonary Clinic, Ambulatory Care Center, Albuquerque, NM  Finished product:  13C-urea Breath Test Kit		Tabulated Study Protocol	
Active ingredient:  13C-urea			
Protocol date HRPO# 29 November 2012 12-521		Planned study period January 1, 2013-March 31,2013	

a single 20 mg dose and 3 will each receive a single 50 mg dose. After the safety of the 50 mg dose has been evaluated, 3 subjects with CF will each receive a single 20 mg dose and 3 subjects with CF will each receive a single 50 mg dose. Three healthy volunteers diagnosed with *H. pylori* infection will also each receive a 50 mg dose to assess potential interference of urease producing bacteria in the stomach. Three additional subjects will be added to every dose level at which a dose-limiting adverse event occurs; no more than 30 subjects will be enrolled. This sample size is based upon a dose-escalation model, not a calculation of statistical power.

**Study Sites and Location:** The study will be conducted at a single center at the University of New Mexico Hospital, Pediatric/Adult Pulmonary Clinic, Ambulatory Care Center, Albuquerque, NM.

# LIST OF ABBREVIATIONS AND DEFINITIONS OF TERMS

Abbreviation	Term
AE	adverse event
CF	cystic fibrosis
CFR	Code of Federal Regulations
COPD	chronic obstructive pulmonary disease
CRF	case report form
DLT	dose-limiting toxicity
FDA	Food and Drug Administration
$FEV_1$	forced expiratory volume in 1 second
FVC	forced vital capacity
GCP	Good Clinical Practice
ICH	International Conference on Harmonization
IEC	Independent Ethics Committee
IRB	Institutional Review Board
MedDRA	Medical Dictionary for Regulatory Activities
SAE	serious adverse event
SAR	suspected adverse reaction
SSAR	serious suspected adverse reaction
TEAE	treatment-emergent adverse event
WFI	water for injection

# 1. INTRODUCTION

## 1.1 CYSTIC FIBROSIS

Cystic fibrosis (CF) is a genetic disease which affects approximately 30,000 people in the United States. Prior to the development of therapies, most people with CF died in childhood. New advances in therapies have increased the average lifespan to about 35 years with respiratory failure continuing to be the primary cause of death.

The CF gene that codes the CF protein (cystic fibrosis transmembrane conductance regulator [CFTR]) was discovered in 1989. CFTR is a protein that regulates the flows of ions, including chloride and bicarbonate, across membranes.

One consequence of abnormal CFTR is that glandular fluids thicken, which leads to obstruction of the ducts. In the pancreas, this obstruction blocks the release of digestive enzymes into the gastrointestinal tract, resulting in poor absorption of nutrients. Patients with CF take replacement pancreatic enzymes before every meal to aid digestion and absorption.

In the lungs of patients with CF, thickened layers of fluid lining the airways obstruct the removal of bacteria. Bacteria that are normally present in healthy lungs, and that are normally washed out by movement of thin layers of surface fluid, are not cleared easily from lungs of patients with CF. Urease-producing bacteria *Staphylococcus aureus* and *pseudomonas* are the most prominent bacteria found in increased numbers in lungs of patients with CF. As bacterial loads increase, patients with CF start to develop mildly increased symptoms such as cough, but they generally do not develop the dramatic signs of lung infection seen in healthy patients who have sudden increases in bacteria that develop into pneumonia.

Patients with CF are followed in CF centers where the insidious nature of increasing bacterial loads is followed by routine sputum or throat cultures at least every three months. The bacterial profile of each patient is known and used to guide aggressive antibiotic therapy for exacerbations. All bacteria are not cleared with antibiotic therapy, but it is believed that antibiotic therapy decreases bacterial burden. It is further believed that patients with CF would experience fewer or less severe exacerbations if more timely antibiotic therapy was administered in advance of exacerbations. To date, however, the timing of these exacerbations cannot be predicted.

